**Statistical analysis plan (SAP) for the (cost-)effectiveness of:
an innovative, personalised intervention of therapeutic Virtual
Reality (VR) IntEgrated within physioTherapY for a subgroup of
complex chronic low back pain (CLBP) patients (VARIETY-study)**

Publication date: 27-01-2023

Sponsor: ZonMw (10270032021502)

Document version: 1.0

Trial registration: ClinicalTrials.gov (ID: NCT05701891)

Main applicant:

[name], HAN

Principal investigator:

[name], HAN

Co-applicants:

[name], VU

[name] [name], Maastricht University

[name] [name], HAN

[name] [name], Radboudumc

[name] [name], Radboudumc

Study objectives and outcomes

Main objective

- To evaluate the effectiveness of physiotherapy with integrated multimodal VR for patients with complex CLBP, compared to usual primary physiotherapy care on physical functioning evaluated by the Oswestry Disability Index (ODI) at 3 months (primary end-point) and 12 months follow-up.

Secondary objective

- To evaluate the effectiveness of physiotherapy with integrated multimodal VR for patients with complex CLBP, compared to usual primary physiotherapy care on secondary outcome measures pain intensity, pain related fears, pain self-efficacy, physical activity level, global perceived effect and problems with activities at 3 months (primary end-point) and 12 months follow-up.
- To evaluate the cost-effectiveness of physiotherapy with integrated multimodal VR for patients with complex CLBP, compared to usual primary physiotherapy care for the 12-month period.

Trial methods

Design

- This study is a pragmatic, multicenter, two-arm, parallel, superiority, cluster-randomized controlled trial. Outcome variables will be measured at baseline, after 1 month (T1; during treatment), 3 months (T3; directly post-treatment), 6 months (T6; 3 months post-treatment) and 12 months (T12; 9 months post-treatment) follow-up, as described in table 1.

Randomization

- Eligible physiotherapists will be randomized on practice level using an online software program and stratified for completion of the three-year master to specialize as a psychosomatic physiotherapist.

Allocation

- Patients will be treated by their physiotherapist and follow the intervention their physiotherapist was randomized to.

Blinding

- Patients cannot be blinded, but will only be informed about their own intervention and will neither be informed about the presence of two arms in the trial nor the intervention received in the other arm.

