- Participating patients will be described using the following baseline characteristics: age, sex, BMI, tobacco use, duration of complaints, comorbidities, occupation, education level, diagnostic and therapeutic procedures in past 6 months, medication use and experience with VR for treatment and entertainment, as shown in table 2. Moreover, participants will be described using the following clinical outcome measures: physical functioning, pain intensity, pain related fears, pain self-efficacy, physical activity level, problems with activities and intervention expectations.
- Participating physiotherapists will be described using the following baseline characteristics: age, gender, number of years' experience as a physiotherapist and specialization (i.e. finished with a master's degree), as shown in table 3.

Process evaluation

- The following process parameters regarding the physiotherapy treatment will be monitored by the physiotherapists for both arms: number of sessions, duration of sessions, applied treatment modality per session and adverse events (if applicable).
- In the experimental arm, the following VR related parameters will be additionally monitored using an online dashboard: treatment modality, daily treatment duration and VAS pain score (before and after VR use).

Analysis

Primary analysis

- The primary analysis will be an intention-to-treat, longitudinal mixed-model analysis comparing the effectiveness of physiotherapy with integrated multimodal VR for patients with complex CLBP, compared to usual primary physiotherapy care on physical functioning at 3 months (primary end-point) and 12 months follow-up.
- All participants in this study will be analyzed using mixed-models with maximum likelihood estimation.
- The analysis will be adjusted for important prognostic characteristics that potentially confound the treatment effects (e.g. physical functioning, pain severity, pain-related fears, BMI, tobacco use) and the baseline value of the outcome measure, with addition of other patient and/or physiotherapist characteristics that substantially differ between the two arms at baseline.

Secondary analysis

- Clinical effectiveness on secondary outcome measures:

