 - The secondary effectiveness analysis will be performed similarly as the primary effectiveness analysis: an intention-to-treat, mixed-model analysis, to evaluate the effectiveness of physiotherapy with integrated multimodal VR for patients with complex CLBP, compared to usual primary physiotherapy care on pain intensity, pain related fears, pain self-efficacy and problems with activities at 3 months (primary end-point) and 12 months follow-up.

Cost-effectiveness

- Health-related Quality of Life: At baseline, 3, 6, and 12 months after start of the intervention, the participants' health states were assessed using the EuroQol 5D Health Questionnaire 3-level version (EQ-5D-5L). Using the Dutch EQ-5D-5L tariff, these health states were converted into utility values (0=dead; 1=full health). Quality-adjusted life-years (QALYs) were calculated using the area under the curve approach.
- Costs: In line with Dutch guidelines, costs were assessed from a societal perspective, meaning that all costs were included irrespective of who paid or benefited.

- Data on other healthcare utilization, informal care, unpaid productivity, and absenteeism. For the cost-utility and -effectiveness analyses, all participants included in the study will be analyzed, with missing data handled by using Multivariate Imputation by Chained Equations (MICE) and the number of imputed datasets will be determined using the loss of efficiency approach. Imputation models will include all available cost and effect measure values as well as variables differing between groups at baseline, variables related to the “missingness” of data and variables related to the outcomes. Pooled estimates will be calculated using Rubin’s rules.

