- Costs and effect differences will be estimated using Seemingly Unrelated Regression analyses, in which their possible correlation can be accounted for. The 95% confidence intervals surrounding the cost differences will be estimated using Bias-Corrected and Accelerated (BCA) bootstrapping. Subsequently, Incremental Cost-Effectiveness Ratios (ICERs) will be calculated by dividing the differences in costs by the differences in QALYs. Uncertainty surrounding the cost-differences and ICERs will be estimated using bias correct and accelerated (BCA) bootstrapping techniques (5000 replications) and be graphically illustrated by plotting BCA-bootstrapped cost-effect pairs on cost-effectiveness planes. Also, cost-effectiveness acceptability curves will be constructed to provide an indication of the probability of physiotherapy with integrated multimodal VR therapy being cost-effective with usual care at different values of willingness to pay.

Responder analysis

- The proportion of participants with a minimal clinically important difference (MCID), responders, on each of the outcome variables between treatment arms, at 3 months and 12 months follow-up:
 - 8 points improvement on the ODI (Hung et al., 2018)
 - 15% and/or 1-point improvement on the NRS (Salaffi et al., 2004)

Availability of data and materials

- The datasets generated and analyzed during the current study will be available in the Dataverse repository.
- The research protocol is accessible at ClinicalTrials.gov (ID: NCT05701891).

Figure 1. *Flow of participants*

[figure not shown]

Table 1. *Overview of measurements*

	T0	T1	T3	T6	T12
Primary outcome measure					
Oswestry Disability Index (ODI)	X	X	X		X
Secondary outcome measure					
Numeric Rating Scale (NRS)	X	X	X		X
Fear Avoidance Beliefs Questionnaire (FABQ)	X	X	X		X
Pain Catastrophizing Scale (PCS)	X	X	X		X
Physical activity (self-reported)	X	X	X		X
Global perceived effect (GPE)		X	X		X
Patient-specific complaints questionnaire (PSK)	X		X		X
Pain self-efficacy (PSEQ)	X	X	X		X
Credibility and expectancy questionnaire (CEQ)	X	X			
Igroup presence questionnaire (IPQ)		X	X		
Economic parameters					
Quality-adjusted life years (QALY) (EQ-5D-5L)	X		X	X	X
Health-related and work-related costs	X		X	X	X
Patient characteristics	X				
Treatment parameters					
Other treatment than PT because of LBP, in past 12 weeks			X		
Duration of PT-treatment (number of weeks/sessions, reported by PT)			X		

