Costs during 12-month follow-up period*	Experimental group (n=), mean costs in € (SE)	Control group (n=), mean costs in € (SE)	Crude mean cost difference in € (SE)	Adjusted* mean cost difference in € (SE)
Intervention-related costs				
Primary health care costs (other than intervention) ^a				
Secondary health care costs ^b				
Medication costs ^c				
Presenteeism costs				
Absenteeism costs				
Unpaid productivity costs				
Informal care costs				
Total costs				

SE = standard error, CI = confidence interval.

*adjusted for treatment arm, baseline costs, QALY, work status, gender, age

- a. primary health care, other than the (experimental or control) intervention (e.g., general practitioner, acupuncturist);
- b. secondary health care (e.g., hospital, rehabilitation center);
- c. (prescribed and over-the-counter) medication for low back pain.

Table 6. *Cost-effectiveness analysis*

Analysis	Sample size		Outcome	ΔC (95 % CI)	ΔE (95 % CI)	ICER	Distribution CE-plane (%)			
	EXP	CON		€	Points		€/point	NE ^a	SE ^b	SW ^c
Main analysis— imputed dataset			ODI (0-100)							
			NRS pain (0-10)							
			QALYs (range: 0–1)							
SA1—health care perspective			ODI (0-100)							
			NRS pain (0-10)							
			QALYs (range: 0–1)							
SA2—human capital approach			ODI (0-100)							
			NRS pain (0-10)							
			QALYs (range: 0–1)							
SA3—complete cases for cost outcomes only			ODI (0-100)							
			NRS pain (0-10)							

Analysis	Sample size		Outcome	ΔC (95 % CI)	ΔE (95 % CI)	ICER	Distribution CE-plane (%)			
	EXP	CON		€	Points	€/point	NE ^a	SE ^b	SW ^c	NW ^d
			QALYs (range: 0–1)							
SA4-a – per protocol cases only (excluding major protocol violators only)			ODI (0-100)							
			NRS pain (0-10)							
			QALYs (range: 0–1)							
SA4-b– per protocol cases only (excluding major and minor protocol violators)			ODI (0-100)							
			NRS pain (0-10)							
			QALYs (range: 0–1)

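### The Table 5 footnote adjusts costs for QALY with no time point, and the Cost-effectiveness section names no baseline covariate for the QALY, ODI and NRS equations (secondary economic analysis, minor)

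*SAP*

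**What the plan says.** Table 5 of the SAP has a crude and an adjusted column for the cost difference. Its footnote describes the adjusted one as "adjusted for treatment arm, baseline costs, QALY, work status, gender, age". Only costs carries the word baseline directly.

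The Cost-effectiveness section says of the QALY: "Quality-adjusted life-years (QALYs) were calculated using the area under the curve approach". The EQ-5D-5L is taken at baseline, 3, 6 and 12 months. In Table 1 the row for this questionnaire opens with "Quality-adjusted life years (QALY) (EQ-5D-5L" and is marked at T0 as well as at T3, T6 and T12.

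On the model, the same section says: "Costs and effect differences will be estimated using Seemingly Unrelated Regression analyses, in which their possible correlation can be accounted for". It lists no covariates for either equation. Baseline variables appear there only for the missing data: "Imputation models will include all available cost and effect measure values as well as variables differing between groups at baseline". Table 6 reports a cost difference, an effect difference and an ICER for ODI, NRS pain and QALYs, and shows no adjustment set.

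For the clinical outcomes, the Primary analysis section adjusts the mixed model for prognostic characteristics and "the baseline value of the outcome measure". The secondary clinical outcomes follow the same approach.

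**The concern.** There are two linked gaps in the economic analysis.

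- **The cost covariate.** A QALY defined as a 12-month area under the curve has no baseline value. An analyst who codes the footnote as it stands would put a follow-up outcome on the right-hand side of the cost model. The arm coefficient would then leave out any cost effect of the intervention that runs through better or worse health.
- **The effect equations.** The QALY contains baseline utility by construction and is also correlated with it through the follow-up utilities. If costs are adjusted for baseline and effects are not, numerator and denominator of the ICER rest on different adjustments, and precision is given away in the effect difference. Chance baseline imbalance is plausible here. The sample is 120 patients of 20 physiotherapists, and the Randomization section says: "Eligible physiotherapists will be randomized on practice level using an online software program".

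**Working it through.** The SAP gives no figure to reproduce on this point. The check compares the passages and then sizes the consequence.

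**Where could effect adjustment come from?**
- The imputation models use baseline variables to fill in missing values. That does not adjust the arm contrast estimated afterwards.
- The baseline rule in the Primary analysis section covers the mixed models, not the seemingly unrelated regression.
- The Table 5 footnote is attached to costs. If its list served the effect equations too, it would still hold no baseline ODI or NRS. Read literally, it would also put the QALY on both sides of its own equation.

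**Weights in the QALY.** The trapezoid rule over 0, 0.25, 0.5 and 1 year gives weights 0.125, 0.25, 0.375 and 0.25. Baseline utility has 12.5% of the weight and follow-up 87.5%.

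**Precision of the QALY difference, clustering ignored.** Assumptions, not in the SAP: equal utility SD at all times, baseline to follow-up correlation r of 0.4 to 0.6, and correlation between follow-ups q of 0.6 to 0.7. In units of the utility SD:
- Cov(QALY, baseline) = 0.125 + 0.875r, which is 0.475 for r = 0.4 and 0.65 for r = 0.6.
- Var(QALY) = 0.28125 + 0.21875r + 0.5q, which is 0.71875 for (0.4, 0.7) and 0.7125 for (0.6, 0.6).
- Correlation = 0.475/√0.71875 = 0.56, or 0.65/√0.7125 = 0.77.
- Cut in standard error = 1 − √(1 − correlation²) = 17% or 36%. The other two pairs of r and q give 19% and 33%.

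**With clustering.** This was simulated with 120 patients, ICC 0.05 and least squares with and without baseline utility. The cut is about 10-43% for 20 clusters of 6 and about 6-48% for 10 clusters of 12. The SAP does not give the number of practices. The low end assumes cluster effects unrelated between baseline and follow-up, and the high end assumes fully persistent ones.

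**ODI.** With the same formula and an assumed baseline to follow-up correlation of 0.4 to 0.6, the cut is 1 − √(1 − 0.16) = 8% to 1 − √(1 − 0.36) = 20%.

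**Literal reading of the cost covariate.** Assume a utility gain of 0.05 from month 3 on, so a QALY gain of 0.05 × 0.875 = 0.04375. Assume costs fall by EUR 0, 5,000 or 10,000 per QALY gained. The adjusted cost difference then omits 0.04375 times that slope, which is EUR 0, 219 or 438, and this counts against VR. On the baseline reading the distortion is zero.

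**The case against.** A reader might infer from the footnote that costs will be adjusted for the follow-up QALY. The documents do not support that. Table 1 uses QALY as its label for the EQ-5D-5L and marks it at T0, the word baseline can carry over from costs to the next item, and the other patient covariates are baseline ones. The euro figures above therefore belong to the less likely reading and rest on assumed inputs.

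A reader might also infer that the plan leaves the effects unadjusted, or that the ICER is biased. Neither follows. The SAP is silent on the matter. Its text names no covariates for costs either, yet a table footnote supplies them, so silence in the text does not mean no adjustment. The visible text ends inside Table 6, and the notes to markers a to d are not shown. The protocol, which the SAP says defines all analyses, is not at hand. Under randomisation an unadjusted difference is unbiased in expectation. A chance imbalance of one standard error is already within its confidence interval, so counting that shift in addition to the lost precision would count one thing twice.

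One could add that a utility imbalance would go unseen, because the listed baseline clinical measures are "physical functioning, pain intensity, pain related fears, pain self-efficacy, physical activity level, problems with activities and intervention expectations", without the EQ-5D-5L. That is a matter of reporting and changes no estimate. Baseline ODI and NRS do appear by arm in Table 4, beside adjusted clinical differences.

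What stands against these objections is that one covariate has two readings with different meanings, and that nothing visible gives the effect equations their baseline values. A list shared between the equations might give the QALY equation baseline utility, but not the ODI and NRS equations theirs.

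**Conclusion.** The point holds as a minor fault of specification in the secondary economic analysis. The footnote names a covariate that the SAP itself defines as a follow-up outcome, and the methods text fixes no baseline covariate for the QALY, ODI and NRS equations. The likely cost is precision, not bias: about 17-36% of the standard error of the QALY difference under the assumed correlations without clustering, and a wider range (about 6-48%) once clustering is allowed for. Adjustment reduced the standard error in every scenario examined. The distortion of the cost difference is zero if baseline utility is meant. Confidence is medium, because notes under Table 6 or the protocol may say more.

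**What to change.** 1. In the Table 5 footnote, replace QALY with baseline EQ-5D-5L utility (T0).
2. In the Cost-effectiveness section, state that the QALY equation of the seemingly unrelated regression is adjusted for baseline EQ-5D-5L utility, and the ODI and NRS equations for their own baseline values.
3. State that Table 6, the ICER and the cost-effectiveness plane use these adjusted differences.
4. Optionally, show baseline EQ-5D-5L utility by arm in Table 2.

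The cost is a few lines of SAP wording, best settled before database lock. Table 1 already schedules the EQ-5D-5L, ODI and NRS at T0, so no new measurement and no change to design or sample size is needed.
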